3.2.3 Procedure and parameters

Prior to performing the liposuction procedure, local anaesthesia is administered using the LipoFlow peristaltic mode. Tumescent fluid usage is 150 cc to 500 cc for a $10 \times 10 \text{ cm}^2$ area, while the anticipated total mg/kg dosage of tumescent lidocaine should not exceed 45 mg/kg.

Approximately 20–30 minutes should be allowed to enable an adequate diffusion of the tumescent solution and provide effective vasoconstriction.

Liposuction with the LipoLifeTM system involves simultaneous work of laser and suction. Alma 1470 diode laser is used in Continuous Wave (CW) emission mode, Pulse mode and Repeat mode. Power settings are recommended to be selected as a function of the liposuction area: 10-13W (chin, arms and knees), 13W (abdomen, back), and 15W (thighs, hips and buttocks). The laser energy is conveyed into the fat layer using a 3mm cannula which incorporates a 400 or $600\mu m$ optical single-use fiber. The suction tube is connected directly to the cannula so laser and suction will work simultaneously.

The LipoLifeTM system is designed to be operated only by licensed medical practitioners properly trained in its handling and use. Personnel operating the device must read the operator's manual.

4 Study Objectives

4.1 Primary objective:

To evaluate the efficacy of Laser Assisted Liposuction procedure with the LipoLife TM system.

4.2 Secondary objectives:

- To evaluate the efficacy of facial fat grafting procedure using autologous fat harvested with the LipoLifeTM system.
- To evaluate subjects' satisfaction.
- To evaluate procedure related safety.
- To evaluate fat vitality of the harvested fat with the LipoLifeTM system (optional).

5 Study Design

This is a multi-center, prospective, open label, single arm study.

The study will include 6 visits at the medical center: screening, pre-surgery evaluation visit, laser assisted liposuction surgery w/wo facial fat grafting and 3 follow up visits.

Following the screening visit, eligible subjects will be enrolled into the study. Each subject will undergo laser assisted liposuction surgery w/wo facial fat grafting (5-20 subjects), using the LipoLifeTM system. Pre-surgery evaluation visit will be carried out 1 week prior to the surgery. Follow up visits to evaluate safety and efficacy will take place at 1, 3 and 6 months after the surgery (See Figure 5 for an illustration of the study design).

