9.7.2 Assessment of Causality

The investigator is obligated to assess the relationship between investigational device and the occurrence of each AE/SAE. The investigator will use clinical judgment to determine the relationship. Alternative causes, such as natural history of the underlying diseases, concomitant therapy, other risk factors, and the temporal relationship of the event to the investigational product will be considered and investigated. The investigator will also consult the IB and/or device information in the determination of his/her assessment.

The causal relationship to the study product assessed by the Investigator (or medically qualified delegate) should be assessed using the following classifications:

Not Related In the Investigator's opinion, there is not a causal relationship between the study product and the adverse event.

Unlikely The temporal association between the adverse event and study product is such that the study product is not likely to have any reasonable association with the adverse event.

Possible The adverse event could have been caused by the study participant's clinical state or the study product.

Probable The adverse event follows a reasonable temporal sequence from the time of study product administration, abates upon discontinuation of

the study product and cannot be reasonably explained by the known characteristics of the study participant's clinical state.

Definitely

The adverse event follows a reasonable temporal sequence from the time of study product administration or reappears when study product is reintroduced.

10 Statistical Analysis

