10.3 Safety Analysis

A detailed list of all adverse events will be presented. The adverse event rate and incidence will be compiled with respect to frequency, nature, seriousness of the event, severity of the event, and relationship to the study device. In addition, listings of all safety measures will be produced.

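### In section 9.7.2 the top causality grade, 'Definitely', is easier to meet than 'Probable', so the grades do not rank how certain a device relationship is

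*Combined protocol and SAP*

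**What the plan says.** Section 9.7.2 asks the investigator to judge how each adverse event relates to the device, taking other causes and timing into account. It then says that causality "should be assessed using the following classifications" and lists five grades. The ones that matter here are:

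- **Not Related**: the investigator's opinion is that "there is not a causal relationship between the study product and the adverse event".
- **Possible**: "The adverse event could have been caused by the study participant's clinical state or the study product". No timing condition is stated.
- **Probable**: three conditions joined together. Timing is plausible, the event abates once the product is stopped, and the clinical state does not account for it (the event "cannot be reasonably explained by the known characteristics of the" subject's condition).
- **Definitely**, the top grade, reads: "The adverse event follows a reasonable temporal sequence from the time of study product administration or reappears when study product is reintroduced". Two conditions joined by 'or', with no condition about other explanations.

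Section 5 plans six visits, with a single operation: "laser assisted liposuction surgery w/wo facial fat grafting and 3 follow up visits". No repeat procedure is scheduled. Section 4.2 lists as a secondary objective "To evaluate procedure related safety". Section 10.3 compiles adverse events by frequency, nature, seriousness, severity "and relationship to the study device".

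**The concern.** A causality scale should become harder to satisfy as it moves up. Here the top step is the easier one: it drops two of the three 'Probable' conditions and offers a second route in. An investigator who applies the definitions literally can place one event in more than one grade, and nothing says which grade prevails. Two investigators, or the two sites, could record the same well-timed event with a plausible clinical explanation as 'Possible' and as 'Definitely'.

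At stake is the breakdown by device relationship in 10.3, which is part of how the safety objective is reported. If the grades are not ordered, a count of 'Definitely' events cannot be read as the most certain device-related events. With about 20 subjects, a few events graded differently would visibly change that breakdown.

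**Working it through.** The plan gives no figure on this point, so there is none to reproduce. The check is a truth table built from the definitions in 9.7.2.

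**Inputs.** T = plausible timing; A = abates on discontinuation; N = not reasonably explained by the clinical state; R = reappears on reintroduction.

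- Definitely = T or R
- Probable = T and A and N
- Possible = T and not N. This is an assumption: both causes are plausible, and the timing condition is supplied because the text has none.

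**Step 1: one surgery, as in section 5.** R cannot occur, which leaves 2 × 2 × 2 = 8 patterns.

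| T | A | N | Definitely | Probable | Possible |
|---|---|---|---|---|---|
| yes | yes | yes | yes | yes | no |
| yes | yes | no | yes | no | yes |
| yes | no | yes | yes | no | no |
| yes | no | no | yes | no | yes |
| no | either | either (4 patterns) | no | no | no |

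'Definitely' covers 4 patterns. The 1 'Probable' pattern and both 'Possible' patterns lie inside those 4. In 2 of the 4, the clinical state offers another explanation.

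**Step 2: is the single surgery the cause?** Allow R, which gives 16 patterns. Definitely = 16 − 4 (neither T nor R) = 12. Probable = 2 and Possible = 4, and all of these still lie inside 'Definitely'. The overlap therefore comes from the 'or' and the missing N condition.

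**Step 3: what the single surgery adds.** Reintroduction does not arise, and discontinuation has no clear meaning for a completed operation. If A is treated as inapplicable, T and N give 4 patterns: 'Definitely' covers 2, 'Probable' 0, and 'Possible' 1, which lies inside 'Definitely'.

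**Step 4: the literal reading of 'Possible'.** Taking its 'or' at face value (T or not N), 'Possible' covers 8 − 2 = 6 of the 8 patterns in Step 1, including all 4 'Definitely' patterns.

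**Step 5: do small edits work?**

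- Change 'or' to 'and' in 'Definitely' (T and R): 0 of 8 patterns after one surgery, so the grade cannot be reached.
- Define 'Definitely' as T and N: 2 of 8. The overlap with 'Possible' (T and not N) falls to 0, but the 1 'Probable' pattern still lies inside 'Definitely'.
- Drop the discontinuation and reintroduction tests and separate the top two grades by E = available clinical evidence directly supports the device as cause. T, N and E give 8 patterns. Definitely (T, N, E) = 1; Probable (T, N, not E) = 1; Possible (T, not N) = 2; all three pairwise overlaps = 0. The 4 patterns without plausible timing are left to 'Unlikely' or 'Not Related'.
- Make that last change but leave the present 'Possible' wording: on the literal reading it covers 6 of 8, including the new 'Probable' and 'Definitely' patterns. 'Possible' must therefore be reworded too.

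**The case against.** The strongest reply is that 9.7.2 must be read as a whole. Alternative causes are to be considered and investigated for every event, and clinical judgment decides. An investigator who follows that would be unlikely to record 'Definitely' for an event that the clinical state explains. This stands as a limit on the practical effect, but it does not separate the grades: the instruction is tied to no particular grade, and a well-timed event with another plausible cause still matches two of them.

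The second reply is that little depends on the grade. This largely stands. Section 10.3 does not say that all five grades will be tabulated. If 'Possible', 'Probable' and 'Definitely' were pooled as related, these boundaries would change nothing. Every event is listed individually and the analysis is descriptive. Notification of serious adverse events under 9.6 does not depend on causality. Section 11.12 adds a report for serious adverse device effects but names no grade, and the stopping text in 11.11 refers to the number and severity of events. The loose wording also leans towards attributing events to the device, which does not hide risk.

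Two stronger readings are tempting. A reader might infer that the single surgery creates the overlap with 'Possible'; Step 2 shows that it does not. A reader might also infer that 'Definitely' will in practice mean timing alone and that 'Probable' will never be used. The documents do not support that: the judgment clause applies to every event, and if abating is read as the event resolving, 'Probable' keeps 1 of 8 patterns.

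**Conclusion.** The definitions are mis-ordered as written and should be reconciled. That 'Probable' lies wholly inside 'Definitely' follows from the text with no assumption. The overlap with 'Possible' assumes only that a well-timed event with another plausible explanation belongs in 'Possible'; the literal reading makes the overlap larger.

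The consequence is small: one descriptive breakdown in about 20 subjects, with a tendency to over-attribute events to the device. The pattern counts describe the logic of the definitions and do not estimate how many events would be misgraded. A reader might infer that the safety conclusions or the trial's reporting obligations are compromised; the documents do not support this, because no efficacy, sample-size, reporting or stopping rule refers to the grade.

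**What to change.** In 9.7.2 and on the adverse event form, remove the discontinuation and reintroduction tests and replace the top three grades with wording such as:

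- *Possible: timing after use of the study device is plausible, but the subject's clinical state, concomitant therapy or other risk factors could also reasonably explain the event.*
- *Probable: timing is plausible and those other causes do not reasonably explain the event, but it does not meet Definitely.*
- *Definitely: meets both Probable criteria (timing and no other reasonable explanation) and, in the investigator's judgment, the available clinical evidence, such as the examination already performed at each visit, directly supports the study device as the cause.*

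Add that each event receives one grade and that no additional imaging or laboratory test is required. That last point matters because no postoperative laboratory test is scheduled and MRI is planned only for the five US subjects.

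The cost is a wording change, ideally made before events are graded, with no extra visits, tests or staff. Fewer events will be graded 'Definitely'. The change still grades relationship to the device, as 10.3 requires. It does not add a separate grade for relationship to the procedure, for example for events after facial grafting, which section 7.3.2 performs with standard equipment.

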10.1 General Considerations

When statistical tests are performed, they will be two-sided. The required significance level of findings will be equal to or lower than 5%. Where confidence limits are appropriate, the confidence level will be 95%.

Baseline values are defined as the last valid value prior to the surgery.

All statistical analyses of safety and performance measures will be descriptive in nature. Continuous variables will be summarized by a mean, standard deviation, minimum, median and maximum, and categorical variables by a count and percentage. Confidence intervals will be provided where relevant.

10.2 Disposition of Subject

The numbers of subjects who were enrolled and completed each visit of the study will be provided, as well as the reasons for all enrollment discontinuations, grouped by major reason (e.g., lost to follow-up, adverse event, poor compliance). A list of discontinued subjects, protocol deviations, and subject excluded from the efficacy analysis will be provided as well.

10.3 Safety Analysis

A detailed list of all adverse events will be presented. The adverse event rate and incidence will be compiled with respect to frequency, nature, seriousness of the event, severity of the event, and relationship to the study device. In addition, listings of all safety measures will be produced.

10.4 Interim Analysis

An interim report to analyse safety and efficacy will be performed at 3 months Follow-Up. 11 Administrative Procedures

11.1 Investigator Responsibility

Except where the Principal Investigator's signature is specifically required, it is understood that the term 'Investigator' as used in this Protocol and on the CRFs refers to the Principal Investigator or an appropriately qualified member of the staff that the Principal Investigator designates to perform specified duties of the Protocol. The Principal Investigator is ultimately responsible for the conduct of all aspects of the study.

Each Investigator will comply with the local regulations regarding clinical trials and the Investigator responsibilities outlined in the ICH GCP guidelines.

11.2 Ethic committee Approval

The Protocol will be submitted for approval to the Reviewing IRB/ Helsinki/ other ethic committee, and written approval obtained, before study subjects are enrolled. The Investigators will receive all the documentation needed for submitting the present Protocol to the Ethics Committee. A copy of the respective approval letters will be transmitted to the Study Monitor before starting the study. The composition of the Ethics Committee must also be provided to the Study Monitor. If approval is suspended or terminated by the Reviewing Ethics Committee, the Investigator will notify the Study Monitor immediately.

It is the responsibility of the Investigator to report study progress to the Reviewing Ethics Committee as required or at intervals not greater than one year.

The Principal Investigator, or his/her nominee, will be responsible for reporting any serious adverse events to the Ethics Committee as soon as possible, and in accordance with the local guidelines.

11.3 Informed Consent

Before recruitment and enrollment into the study, each prospective candidate will be given a full explanation of the nature and purposes of the study, and a copy of the Informed Consent Form to review. Once the essential study information has been provided, and the Investigator is assured that each potential subject understands the implications of participating in the study, the subjects will be asked to give consent to participate in the study by signing the informed consent form. The consent forms shall

be signed and dated by the appropriate parties. A notation that written informed consent has been obtained will be made on the participant's CRF. The completed consent forms will be retained by the Investigator and a copy of these will be provided by the Investigator to the participant.

11.4 Case Report Forms (CRF)

A Case Report Form (CRF) will be completed for each study subject summarising all clinical screening and study data. Subjects will only be referred to in the CRF by their subject number and initials in order to retain their confidentiality.

The Investigator is responsible for completely and accurately recording study data in the appropriate sections of the CRFs provided by Alma lasers. The CRFs must be signed by the Investigator or by his/her authorized person as designated in the Signature Authorization Log.

The completed original CRF's are to be sent to the Sponsor as soon as practical after completion and review. A copy of each completed CRF is to be retained by the Investigator for a period of time as determined by local regulations.

11.5 Monitoring and Quality Assurance

The task of the Study Monitor is to guarantee the best conduct of the study through frequent contacts by phone and in person with the responsible Investigator, in accordance with the Monitor's Standard Operating Procedures, with the purpose of facilitating the work and fulfilling the objectives of the study. The Monitor is responsible for monitoring adherence to the Protocol and completion of the CRF, and for the relationship between the Investigator and Alma Lasers Ltd.

The organisation, monitoring, supply of study materials and quality assurance of the present clinical study is the responsibility of Alma Lasers Ltd. or its designee.

In order to ensure the accuracy of data, direct access to source documents by the representatives of both the Study Monitor and regulatory authorities is mandatory. Anonymity of the subject will be maintained at all times. Alma Lasers Ltd. reserves the right to terminate the study for refusal of the Investigator/Institution to supply source documentation of work performed in the study.

11.6 Financial Aspects

The conduct of the study is subject to a Financial Agreement between Alma Lasers Ltd. and the Investigator or Institution.

11.7 Device Use/Accountability

Use and storage of LipoLifeTM system and accessories will be performed according to the Operation Manual. All received used and unused LipoLifeTM system components will be documented on the accountability form.

11.8 Protocol Amendments

Neither the Investigator nor Alma Lasers Ltd. will modify the Protocol without first obtaining the concurrence of the other in writing. Protocol modifications that impact on participant safety or the validity of the study will be approved by the Ethics Committee.

No changes (amendments) to the Protocol may be implemented without prior approval from the Sponsor and the Reviewing Ethics Committee. If a Protocol amendment requires changes to the Informed Consent Form, the revised Informed Consent Form, prepared by the Investigator, must be approved by the Reviewing Ethics Committee.

Once the final Protocol has been issued and signed by the Investigator and the authorised signatories, it shall not be informally altered. Protocol amendments are alterations to a legal document and have the same legal status. Therefore, they must pass through appropriate steps before being implemented. In general, any important change that theoretically increases risk to participants constitutes an amendment. Minor changes are administrative changes and need documentation without approval.

It is the responsibility of the Investigator to submit the amendment to the Reviewing Ethics Committee for their approval; written approval should be obtained and a copy provided to the Sponsor. The Sponsor is responsible for determining whether or not the local regulatory authority must be notified of the Protocol change. Completed and signed Protocol amendments will be circulated to all those who were on the circulation list for the original Protocol.

The original signed copy of amendments will be kept in the Study File with the original Protocol. It should be noted that where an amendment to the Protocol substantially alters the study design or the potential risks to the participants, each participant's consent to continue participation should be obtained.

11.9 Protocol Compliance

The instructions and procedures specified in this Protocol require diligent attention to their execution. Should there be questions or consideration of deviation from the Protocol, clarification will be sought from the Study Monitor. Any participant treated in a manner that deviates from the Protocol, or who is admitted into the study but is not qualified according to the Protocol as amended by Alma Lasers Ltd. and the Investigator, may be ineligible for analysis and thereby compromise the study.

Only when an emergency occurs that requires a departure from the Protocol for an individual will there be such a departure. The nature and reasons for the Protocol violation/deviation shall be recorded in the CRF and the investigator should notify the sponsor and Ethics Committee as soon as possible.

11.10 Archives: Retention of Study Records

All source documents, CRFs and trial documentation will be kept by the Investigator for the appropriate retention period as stipulated by local regulations and ICH-GCP.

11.11 Early Termination of the Study

The study may be terminated prematurely by the principal investigator or his/her designee and the sponsor if:

- The number and/or severity of adverse events justify discontinuation of the study
- New data become available which raise concern about the safety of the study device, so that continuation might cause unacceptable risks to subjects.

In addition, Alma Lasers Ltd. reserves the right to discontinue the trial prior to inclusion of the intended number of participants, but intends only to exercise this right for valid scientific or administrative reasons.

After such a decision, the Investigator must contact all participating subjects, and written notification must be sent to the Reviewing Ethics Committee and relevant Regulatory Authorities.

11.12 Reporting Requirements

The investigator must promptly report to Alma lasers any withdrawal of IRB/Helsinki/other ethic committee approval at the site. Additional reporting requirements include:

- Notify Alma Lasers' designee and to the ethic committee a report of any serious adverse device effect, whether anticipated or unanticipated, that occurs during the study as soon as possible, but in no event later than 10 working days after the investigator first learns of the effect. This report is to include a description of the effect, subsequent treatments, clinical outcomes, and outcome diagnoses. If the site personnel are not sure whether an event meets these criteria they should call the clinical monitor.
- Notify Alma Lasers or Alma Lasers' designee and the ethic committee immediately (within 24 hours) if an emergency situation arises in which the subsequent treatment, in the best interests of the subject, requires a deviation from the protocol. This should be followed with written confirmation that describes the emergency action and outcomes, to Alma Lasers and the ethic committee within 5 working days.
- Report to the ethic committee and Alma Lasers, within 5 working days, the use of the study device without signed informed consent from the subject.
- Report adverse events in accordance with 21 CFR 803.
- Submit regular progress reports to the approval committee and Alma Lasers or Alma Lasers' designee, as requested by the investigators or the ethic committee.
- Submitting a final report on the study to the ethic committee and Alma Lasers or Alma Lasers' designee within 3 months after termination or completion of the study.

12 References

Plastic Surgery Statistics Report. Am. Soc. Plast. Surg. (2017).
 https://www.plasticsurgery.org/documents/News/Statistics/2017/plastic-surgery-statistics-report-2017.pdf (Accessed on March 20, 2018).

- 2. Atiyeh, B. *et al.* Functional and Therapeutic Indications of Liposuction: personal experience and review of the literature. *Ann. Plast. Surg.* **75,** 231–245 (2015).
- 3. Xie, Y. *et al.* An integrated fat grafting technique for cosmetic facial contouring. *J. Plast. Reconstr. Aesthetic Surg.* **63,** 270–276 (2010).
- 4. Charles-De-Sa, L. *et al.* Antiaging treatment of the facial skin by fat graft and adipose-derived stem cells. *Plast. Reconstr. Surg.* **135**, 999–1009 (2015).
